[name] will inform potential participants about the study and study-related procedures. Because [name] provides medical care and/or performs surgical diaphragm pacer implantation to this C-SCI population, he will identify potential participants who meet the inclusion/exclusion criteria. The specified criteria (determination of SCI injury level and status, respiratory function, medical history) are routinely part of this patient population's medical care and medical history. If a potential participant would like to learn more about the study, detailed information will be provided to the patient and their caregivers/family. The informed consent document will be used to guide this process. [name] also will notify the PI, [name] or a study Co-I that a patient would like to learn about the study and may be potentially interested in enrolling. Study coordinators, [name] or [name], who work closely with the study physicians, also may notify [name] and study Co-I. Based on this, [name] and/or a study Co-I will discuss the study with the patient and caregivers/family.

Study design & overview.

A single-factor quasi-experimental time-series study design is proposed. We will systematically evaluate diaphragm activation from EMGs recorded from intramuscular pacing electrodes and test inspiratory muscle strength and respiratory function in a small group of patients with acute, C-SCIs who have undergone implantation of diaphragm pacing electrodes.

An overview of the assessments is below, with details outlined in the subsequent sections.

Assessment Overview: We will study a small cohort of patients with acute C-SCIs following implantation of intramuscular diaphragm pacing wires. All individuals will meet inclusion criteria and will complete the informed consent process. Experiments are designed to determine if diaphragm stimulation (pacing) can produce neuroplastic changes in respiratory neural drive to the diaphragm and increase respiratory function. Neural drive to the diaphragm will be assessed by recording electromyograms (EMGs) from the intramuscular pacing wires following each of 3 blocks of diaphragm stimulation (Figure 3). Concurrent with these recordings from the diaphragm, respiratory function will be assessed using standardized clinical respiratory measures.

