[name] will provide medical oversight of procedures. Assessments will be conducted by the PI, [name] and/or [name] and [name], DPT. A study research assistant may assist with the assessments. The study team has extensive experience with these assessments. Assessments are conducted in the intensive care unit, with the patient's care team easily accessible.

Given the medical condition of these participants, we will adjust timing or omit a test if necessary, as to not interfere with the participant's medical care. Furthermore, the timing of tests and duration of stimulation may vary slightly given the constraints of patients being in the intensive care unit (ICU) and coordination with nurses, physicians, and ICU scheduling. Additionally, these parameters may vary based on the safety and medical monitoring of each subject as directed by [name].

During the assessments, photographs and/or video recordings may be obtained. These recordings will be done with the participant's knowledge and consent for the type of recording being obtained. Photographs and video recordings will be used to communicate study procedures with the study team and to monitor the assessment process. Video and photographic data will be used to assess how individuals with SCIs perform and respond to the testing and to communicate the study procedures. Video and photographic information will be used in a manner based on the level of consent obtained from each participant.

Diaphragm Stimulation: This protocol will not alter the implantation of the diaphragm pacer. This study will assess those who have received or who are planned to receive the device based on their medical needs and prior medical assessments (not associated with this study). Diaphragm stimulation settings are determined intraoperatively or immediately postoperatively by the surgeon ([name]) to maximize stimulation effectiveness and also to ensure patient comfort. Parameters such as stimulation amplitude, frequency, and breaths per minute are adjusted within a pre-set range based on the device usage guidelines. Typical values are 15-25mA at a frequency of 30 or 50Hz, and at a rate of 12-18 breaths per minute.^{39,40} we expect stimulation parameters to be in this range.

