Assessment of neuromuscular activation of the diaphragm. Neuromuscular activation of the diaphragm will be assessed by recording diaphragm EMGs from the surgically-implanted intramuscular stimulating electrodes.^{11,75} This approach will allow for comparisons of EMG recordings across time and reduces the methodological limitations associated with surface or percutaneous EMG approaches.⁹ EMGs will be recorded during non-stimulated respiration (diaphragm pacer turned off) and simultaneously with assessments of respiratory function. These assessments may include maximal inspiratory pressures and assessments of resting tidal breathing and measurement of flow volumes using standard spirometry.^{76,77}

Primary outcomes to characterize neuromuscular activation of the diaphragm and assess changes in diaphragm activation associated with intramuscular diaphragm stimulation will include: amplitude and timing characteristics (raw, filtered EMGs and normalized);^{76,77} neural respiratory drive to evaluate diaphragm muscle activation during tidal breathing relative to activation capacity during maximal inspiratory maneuvers;^{77,78} and time-frequency characteristics of the diaphragm EMGs (wavelet analysis).^{75,79-81} Methods pertaining to diaphragm EMG signal acquisition and processing are explained below.

Diaphragm EMG acquisition and signal processing. The PI has extensive experience with EMG acquisition and analyses in humans.^{69,70} EMGs will be recorded from the externalized pacing wires which connected to each of four intramuscular electrodes (2 in each hemidiaphragm). The implanted, remote sub-cutaneous electrode will serve as the ground.¹¹ A custom-connector (Synapse Biomedical, Oberlin, OH) will be used to link the exposed pacing wires to our EMG acquisition system. EMG signals will be amplified and band pass filtered (10 Hz to 1000 Hz), acquired at a sampling frequency of 2 kHz, and saved to a computer for off-line analysis.

To acquire the diaphragm EMG signals, the pacer will be shut off to allow connection to the EMG acquisition system. It is feasible to shut off the diaphragm pacer for several reasons.

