First, most of the individuals with SCI have residual respiratory control and are able to maintain sufficient respiration for a short time period. It is part of standard procedures to turn off the pacer on a regular basis to change the pacer batteries. Consistent with this process (turning off the pacer when changing the batteries), supplementary respiratory support will be provided as needed (i.e. mechanical ventilation) and oxygen saturation will be monitored at all times to ensure adequate respiration (>90% O₂ saturation) during the assessments. Second, all assessments will be overseen by the participant's clinical medical team (ICU) with oversight from the participant's physician. All assessments will include cardiorespiratory monitoring. Finally, an assessment will be halted at any time the patient indicates distress or indicates that he or she would like to stop the assessment. In this case, the pacer will be re-connected and turned on and respiratory support will continue until the patient is comfortable.

Neuromuscular activation outcomes. Raw, filtered EMGs, as well as normalized signals will be assessed for timing and amplitude characteristics. Normalization will be based on maximal amplitude of the signals recorded during tests of maximal inspiratory pressure and sniff nasal inspiratory pressure.^{76,78,89} Signals will be full-wave rectification and amplitudes calculated based on the root mean square or integral of the signal. Comparisons of normalized signal amplitudes, burst timing, and burst durations will provide evidence of changes in neuromuscular activation of the diaphragm in association with intramuscular stimulation of the diaphragm and following C-CSI. Increased EMG amplitudes are indicative of greater motor unit recruitment and suggest gains in muscle force generation.^{65,75,90}

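### The plan provides neither for coding the EMG recordings nor for masking the analyst to session, although the primary EMG outcomes are extracted off-line with processing choices left open and coding would cost little.

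*Combined protocol and SAP*

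**What the plan says.** Everything relevant is in section 6 (Research Plan).

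- **Role of the EMG.** Under Assessment of neuromuscular activation of the diaphragm: "Primary outcomes to characterize neuromuscular activation of the diaphragm and assess changes in diaphragm activation associated with intramuscular diaphragm stimulation will include" amplitude and timing measures, neural respiratory drive and time-frequency measures.
- **When the outcomes are derived.** Under Diaphragm EMG acquisition and signal processing, the signals are amplified, filtered, sampled and "saved to a computer for off-line analysis".
- **How they are derived.** Under Neuromuscular activation outcomes, the signals are rectified and "amplitudes calculated based on the root mean square or integral of the signal". The same paragraph says "Comparisons of normalized signal amplitudes, burst timing, and burst durations will provide evidence of changes in neuromuscular activation". No rule for marking a burst is given.
- **Who is involved.** Under Post-tests: "Assessments will be conducted by the PI" and other team members, and "A study research assistant may assist with the assessments". Under Diaphragm EMG acquisition and signal processing: "The PI has extensive experience with EMG acquisition and analyses in humans".
- **Design.** Under Study design & overview: "A single-factor quasi-experimental time-series study design is proposed". There is one group and no sham or control period. Interpretation and possible outcomes declares that greater diaphragm activation after stimulation is expected.

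**The concern.** The staff at the bedside must know whether stimulation has been given, so the tests themselves cannot easily be masked. The off-line step can be. It comes after the session, it yields the primary outcomes, and it involves judgement about segments and bursts. An analyst who knows the session and the expected direction can, without intending to, treat pre and post traces differently.

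In a controlled trial, part of such a shift could cancel between arms. Here the pre/post difference is the whole result, so a processing shift passes straight into it, and a larger sample would not reduce it. The protocol intends a positive finding to support a larger pacing trial, so a change produced by processing could be carried forward as a signal.

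**Working it through.** The plan states no figure on this point, and it gives no alpha, power, effect size or SD, so there is nothing to reproduce. The check compares the relevant parts of the text, counts the workload, and adds one illustration under stated assumptions.

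**1. Is masking provided anywhere?** No section provides for blinding, masking or coding, either of assessors or of files. The word double-blind occurs only in the title of a cited paper. The random ordering of tests (under Assessments of diaphragm muscle strength and respiratory function) is part of standardizing the battery and conceals nothing about the session.

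**2. Which processing steps are fixed, and which are open?**

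| Step | Status in the plan |
|---|---|
| Filter band and sampling rate | Fixed (10 to 1000 Hz; 2 kHz) |
| Neural respiratory drive | RMS fixed |
| Time-frequency analysis | Morlet wavelet and a named base algorithm fixed |
| Normalizing reference | Largest amplitude in the maximal inspiratory and sniff tests |
| Which breaths and effort segments enter | Open |
| Burst onset and offset | Open |
| General amplitude | RMS or integral, open |

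Much of the pipeline is algorithmic. The exposed part is segment choice, burst marking and one metric.

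**3. Does the analyst know the session?** The team running the sessions includes the person credited with EMG analysis expertise. That makes unmasked processing a reasonable inference. The documents do not say who processes the files or how they are labelled.

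**4. Would coding work, and how much work is it?** All EMGs are recorded with the pacer off, and the post-tests repeat the pre-test battery, so the trace itself should not show whether stimulation was given.

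- Sets per participant: 2 (pre-stimulation) + 3 (post-tests) = 5.
- Total: 5 × 5 = 25 for the five targeted completers; 5 × 10 = 50 for ten participants.
- Time from the start of the pre-test to the end of post-test 3, using the durations under Pre-stimulation Assessment and Post-tests: 2 + 1 + 1 + 1 + 1 + 12 + 1 = 19 h at the nominal block lengths, and 2 + 2 + 1 + 2 + 1 + 24 + 1 = 33 h at the maximum lengths.

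Waiting for one participant's full set therefore takes roughly a day or a little more.

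**5. Illustration of sensitivity.** Suppose that processing adds b SD to every post value, where SD is the spread across participants at one session. Assumed, not in the documents: one pre and one post value per participant, normal data, pre/post correlation 0.7, no true effect, two-sided alpha 0.05, exact tests, 20,000 simulated trials. The table gives the proportion of trials declared significant.

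| b (SD) | Mann-Whitney, n=10 | Signed-rank, n=10 | Mann-Whitney, n=5 |
|---|---|---|---|
| 0 | 0.2% | 4.7% | 0.3% |
| 0.25 | 1.2% | 15% | 0.8% |
| 0.5 | 7.7% | 43% | 2.7% |
| 1.0 | 55% | 94% | 16% |

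Mann-Whitney is the test named under Statistical analysis; the paired signed-rank test is shown for comparison. At n=5 the two-sided signed-rank test cannot reach 0.05, since its smallest p is 2/2⁵ = 0.0625. The low Mann-Whitney rates at b = 0 arise because an unpaired test is applied to correlated pairs, which is a separate matter. The table shows what a shift of a given size would do. It says nothing about how large a shift is likely.

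**The case against.** The best case against has four parts.

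**Silence is not conduct.** A reader might infer that the files are labelled and processed by people who know the session. The documents do not say so. They name who conducts assessments and who has EMG experience, and stop there. This stands: the point is the absence of a provision, not a known practice.

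**Coding does not remove the bias.** A reader might also infer that it would. It acts only after acquisition. Coaching and effort in the maximal maneuvers supply the normalizing maximum, and tests may be re-timed or omitted for clinical reasons, all with the session known. This stands too.

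**The direction is not uniform.** It is tempting to say that any bias favours the hypothesis. Neural respiratory drive is tidal RMS divided by the maximal EMG, so choosing a larger tidal segment raises it and accepting a larger maximum lowers it. The plan names no favourable direction for drive, burst timing or burst duration. Only for amplitude is a rise clearly read as benefit.

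**No size is shown, and this is a small proof-of-concept study.** Any percentage inflation needs an assumed number of candidate segments and an assumed variability between them; neither is in the documents. With the planned test at n=10, a shift of 0.25 SD gives only 1.2% false positives in the illustration. This limits the weight of the point but does not answer it: the protection is nearly free, and the results are meant to inform a larger trial.

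**Conclusion.** The concern holds as a gap with a cheap remedy. The primary EMG outcomes are extracted after the session, with segments, burst limits and one amplitude metric left open, in an uncontrolled pre/post design with a declared expectation, and the plan provides for neither coding nor masking. No stated figure or rule is contradicted.

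The size of any bias cannot be estimated from the documents. Under the assumptions above, a moderate shift of 0.5 SD would matter (7.7% false positives with Mann-Whitney and 43% with signed-rank at n=10) and a small one would matter little with the planned test. The conclusion does not depend on those figures. It rests on the absence of a masking provision, on the open choices, and on a workload of 25 to 50 sets.

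The change is worth making before any recording is processed. If coding is already intended, stating it settles the point.

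**What to change.** Under Diaphragm EMG acquisition and signal processing and Neuromuscular activation outcomes, state that:

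- each EMG test set is exported under a random code, with session labels and time stamps stripped, by script or by the research assistant already on the team; the tidal and maximal recordings of one set share a code so that they can still be normalized together;
- selection of breaths and efforts, any exclusion of segments, burst marking and amplitude extraction are done on coded files only;
- either RMS or integral is fixed beforehand for general amplitude, with a written rule for burst onset and offset;
- the code is broken only after the outcome table is locked.

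Add a sentence acknowledging that bedside acquisition and coaching remain unmasked.

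The cost is a renaming step for 25 to 50 sets, a few sentences of text, and a wait until each participant's sessions are complete. It needs no extra staff, and bedside testing and care are unchanged. Fixing the metric and the burst rule limits discretion even without masking, so that part is worth doing in any case.

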Diaphragm EMGs will be recorded from the intramuscular diaphragm pacing electrodes and respiratory function will be assessed during non-stimulated respiration (diaphragm pacing unit turned off). Diaphragm EMGs will be recorded from the intramuscular pacing electrodes with a custom connector that attaches to the external pacing electrode wires and interfaces with an EMG acquisition system. Concurrent with EMG recordings, each assessment will include tests of maximal inspiratory pressures to assess diaphragm muscle strength and maximal activation. Respiratory function also will be assessed by measurement of standard spirometry (tidal breathing, forced vital capacity or FVC).

To classify the level and severity of each subject's C-SCI, a clinical ASIA neurologic examination will be performed in accordance with the International Standards for Neurological Classification of Spinal Cord Injury. This standardized clinical examination will allow us to characterize segmental sensory and motor function.

Baseline Assessments

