After obtaining informed consent for participation in the study, [name] or designated members of the study team ([name], [name], DPT) will review the participant's medical records to obtain study-related medical and demographic data. Information obtained from the medical record will include information pertaining to health and medical history, details pertaining to the SCI, reports of medications and test results that could influence the individual's participation in the research procedures.. Additionally, clinical tests of sensory and motor function will be conducted to classify the level and severity of the individual's SCI. The tests of sensory and motor function are part of the American Spinal Injury Association (ASIA) Impairment Scale and the International Standards for Neurological Classification of Spinal Cord Injury. These clinical assessments are part of standard clinical care and include tests of sensation (dermatomes) and muscle strength via manual muscle testing (myotomes). These routine, standardized tests are done to clinically determine which segmental levels of the spinal cord demonstrate normal or impaired function. These tests also aid in determining if the SCI is clinically complete or incomplete. Determination of complete vs. incomplete is based on the sensory and motor function in the lowest sacral segments which control sensation and motor function at the anal sphincter. These standardized clinical tests are part of routine examination following spinal cord injury.

Baseline respiratory testing will be initiated once per day, up to 3 times on the days prior to diaphragm pacer implantation (Figure 3). Baseline respiratory tests include measurements of standard spirometry (tidal breathing, forced vital capacity or FVC) and maximum inspiratory pressures. We recognize that enrolling patients prior to diaphragm pacer placement may not always be feasible and we, therefore, may enroll participants up to 5-days following pacer implantation and will not obtain baseline (pre-implant) respiratory measures in these individuals.

*Pre-stimulation Assessment (post-diaphragm pacer placement)**

Page 7 of 19

Protocol #: 201902285

IRB version: 10/09/2019

PI version: 2/3/2022

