Following diaphragm pacer placement, the pre-stimulation assessment (prior to turning **on** the diaphragm stimulation) will be initiated approximately 18-24 hours after pacer implantation, once the patient is medically stable and able to participate. Waiting 18-24 hours after pacer implantation is standard of practice based on the procedures used by the diaphragm pacing surgical team ([name]). For individuals enrolled within 5-days after pacer implantation, the pre-stimulation assessment will occur as soon as possible after enrollment. The pre-stimulation assessment will include clinical respiratory tests and recording of diaphragm EMGs which are detailed in sections below. Pre-stimulation assessment will take approximately 2 hours to complete. To obtain a clear pre-stimulation assessment, two sets of tests will be conducted, about 1 hour apart. Ample time for rest breaks will be provided. The participant will be closely monitored and testing will be adjusted for each participant's comfort and medical needs.

*Post-tests (following periods of diaphragm stimulation)**

[figure not shown]
Post-testing will occur after 3 different blocks of diaphragm stimulation, and will occur with the stimulator turned off (Figure 3). These blocks are contiguous, meaning block 2 will begin immediately after post-testing in block 1, and block 3 will begin immediately after post-testing in block 2. See Figure below. Of note, turning the stimulator off and on is a typical occurrence in the medical setting. This allows patients to get used to the stimulation and also is necessary to change batteries in the control box. This externalized control box is easily accessible and has simple controls for turning the unit on and off. Post-tests will include the same battery of clinical respiratory assessments and diaphragm EMGs as pre-testing and will take approximately 1 hour to complete. The duration of stimulation varies for each block:

Block 1: ~1 hour of stimulation (no longer than 2 hours*) followed by post-test 1

Block 2: ~ 1 hour of stimulation (no longer than 2 hours*) followed by post-test 2

Block 3: ~ 12 hours of stimulation (no longer than 24 hours*) followed by post-test 3

Figure 3

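### Does the loosely defined maximum used to normalise diaphragm EMG bias normalised amplitude and neural respiratory drive upward after stimulation?

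*Combined protocol and SAP*

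**What the plan says.** All references are to the combined protocol and SAP, section 6, unless stated otherwise.

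**The denominator.** Neuromuscular activation outcomes states: "Normalization will be based on maximal amplitude of the signals recorded during tests of maximal inspiratory pressure and sniff nasal inspiratory pressure". Amplitude may be the root mean square (RMS) or the integral, and higher amplitude is read as greater motor unit recruitment. Neural respiratory drive is tidal RMS over the maximal EMG from maximal inspiratory manoeuvres, with no sniff named; it is described as a load-to-capacity measure and a severity marker. Raw amplitude, normalised amplitude, timing, neural respiratory drive and wavelet measures are all listed as primary EMG outcomes.

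**The battery.** The Assessment Overview says "each assessment will include tests of maximal inspiratory pressures to assess diaphragm muscle strength and maximal activation", and adds tidal breathing and forced vital capacity. Baseline Assessments says "Baseline respiratory tests include measurements of standard spirometry (tidal breathing, forced vital capacity or FVC) and maximum inspiratory pressures". The EMG section says "These assessments may include maximal inspiratory pressures and assessments of resting tidal breathing and measurement of flow volumes using standard spirometry". Diaphragm muscle strength asks for roughly 3 to 5 repetitions at least 60 s apart, and describes how maximal inspiratory pressure is taken in ventilated subjects. It describes no sniff.

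**The schedule.** Before stimulation, "two sets of tests will be conducted, about 1 hour apart", and "Pre-stimulation assessment will take approximately 2 hours to complete". Afterwards, "Post-tests will include the same battery of clinical respiratory assessments and diaphragm EMGs as pre-testing and will take approximately 1 hour to complete". To protect medical care, "we will adjust timing or omit a test if necessary". Statistical analysis plans a Mann-Whitney U test of pre against post, with no significance level or effect size.

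**The concern.** Three things look wrong.

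- The normalisation names a manoeuvre that the battery does not contain, so two analysts could build different denominators.
- The pre-stimulation assessment offers about twice as many efforts as a post-test. The largest of more efforts is larger on average. If the maximum is taken over the whole assessment, the later denominator is smaller by chance and the ratio rises with no change in the patient. That is the direction the plan reads as a gain.
- When RMS is used with a common maximum, normalised tidal amplitude and neural respiratory drive are the same number. Yet the plan speaks of one as a gain and of the other as a severity marker, and gives no direction of benefit for the second.

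At stake would be a spurious increase in two primary EMG outcomes that favours the study hypothesis.

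**Working it through.** The plan gives no figure to reproduce, so the check asks how large the artefact is under each way of filling the gap.

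**Inputs from the plan.** About 3 to 5 efforts per set; two sets before stimulation; apparently one set per post-test. The last is inferred from the one-hour duration; Figure 3, which sets out the schedule, could not be read in the text available. Pooling the two earlier sets gives 2 × 3 = 6 to 2 × 5 = 10 efforts.

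**Assumed.** Effort-to-effort SD of log maximal EMG of 0.1, 0.2 or 0.3 (the documents give none); independent, normally distributed efforts on the log scale; unchanged tidal EMG.

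**Formula.** Let e(k) be the expected maximum of k standard normal efforts: e(3) = 0.846, e(5) = 1.163, e(6) = 1.267, e(10) = 1.539. The shift in the ratio with no true change is exp(SD × [e(k before) − e(k after)]) − 1. For 6 against 3 at SD 0.2 this is exp(0.2 × 0.421) − 1 = +8.8%.

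| How the maximum is taken | SD 0.1 | SD 0.2 | SD 0.3 |
|---|---|---|---|
| Both earlier sets pooled, 6 v 3 | +4.3% | +8.8% | +13.5% |
| Both earlier sets pooled, 10 v 5 | +3.8% | +7.8% | +11.9% |
| Own set, equal efforts | 0% | 0% | 0% |
| Own set, 3 v 5 | −3.1% | −6.1% | −9.1% |
| One fixed reference per participant | 0% | 0% | 0% |

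**If the maximum truly changes.** The plan expects activation to rise. If maximal EMG rises 20% and tidal EMG does not, equal counts give 1/1.20 − 1 = −16.7%. Pooled 6 v 3 at SD 0.2 gives 1.088/1.20 − 1 = −9.3%. The pooled artefact is cancelled once the true rise reaches 8.8%.

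**Effect on the planned test.** Trials with no true change were simulated with n = 10, two-sided 0.05 (assumed, so 0.025 in the upper tail), tidal noise log SD 0.15 per set, set-level log SD 0 or 0.1, and 3 or 5 efforts per set. With the three effort SDs this makes 12 cells.

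- Pooled rule, between-person log SD of the ratio 0.2: the Mann-Whitney test declares a false increase in 0.006 to 0.079 of trials, at or below 0.025 in 5 of the 12 cells. Own-set rule: 0.001 to 0.009.
- Pooled rule, between-person log SD 0.4: below 0.025 in all 12 cells.
- Pooled rule, n = 5 (the number of successfully tested participants the plan aims for), between-person log SD 0.2, effort SD 0.2, set SD 0.1, 4 efforts: 0.019.
- A paired signed-rank test, which the plan does not use, gives 0.061 to 0.169 under pooling at n = 10 and between-person log SD 0.2, and 0.023 to 0.027 under the own-set rule.

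**The sniff.** It appears once, in the normalisation sentence. The definition of neural respiratory drive needs only maximal inspiratory manoeuvres, and maximal inspiratory pressure is in the battery. If no sniff is recorded, the denominator comes from the maximal inspiratory pressure efforts alone, before and after alike. The Baseline list says nothing on this point, since those tests precede implantation and carry no EMG, and the EMG section's list is permissive.

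**The case for a change.** The best case for acting is that the mismatch can be seen on the page, that the denominator of two primary outcomes should be settled before data are seen, and that a few sentences would settle it at no burden to patients. The pooled reading is also not far-fetched. Participant compensation counts 7 EMG/respiratory assessments, which fits 3 baseline + 1 pre-stimulation + 3 post-tests, so the two earlier sets count as one assessment. Under pooling the estimate is shifted even where the test does not flag it. With no SD assumed, the larger of the two maxima falls before stimulation in 6/(6 + 3) = 67% of comparisons.

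The mismatch and the missing rule stand. The directional claim does not. A payment count does not say how a maximum is computed, and the two sets are there to give a clear pre-stimulation reading, which they do equally well if each is normalised on its own. Any written rule would also have to choose between own-set maxima and one fixed reference. Own-set maxima protect against drift in recording gain but absorb a true rise in maximal EMG; a fixed reference does the reverse. The documents give no figure for either, so this is a trade-off for the investigators. The undeclared direction for neural respiratory drive affects interpretation only: the plan tests for differences, and its own description of the measure tells a reader how to take a rise.

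**Conclusion.** No change to the plan follows. The unlisted sniff test is a small inconsistency, and the source of the maximum is a missing detail that analysts can settle from the stored signals by comparing equal numbers of efforts or using one reference throughout. The upward bias of about 4% to 13% requires pooling that the plan does not state, an unchanged true maximum, one set per post-test and the assumed effort SDs. Other ordinary readings give zero or a negative shift. Raw amplitude is a primary outcome in its own right, so a reader can see whether numerator or denominator moved; raw amplitude, timing and wavelet results are not touched by this denominator. In a proof-of-concept study of about ten participants, with five complete data sets as the target, this is a detail to report clearly with the results.
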